### 13.4 Exploratory Analysis

- Descriptive summaries will be provided for HDSM-Ax and HDSM-Ax, Child, Summary Questions (No. 4 and No. 5) and PGI-S. Mean changes from baseline and observed values will be summarized by time point.
- For HDSM-Ax and HDSM-Ax, Child, the mean of the items in Section No. 1, No. 2, and No. 3 will be calculated for every subject at each time point. The mean will be derived by taking the total score and dividing it by the number of questions answered. Subjects must answer  $\geq 6$  of the 11 sub-items to be evaluable for HDSM-Ax or HDSM-Ax, Child total score. Observed values and changes from baseline at each time point will be summarized and plotted over time using descriptive statistics.
- For the HDSM-Ax or HDSM-Ax, Child Summary Questions (No. 4 and No. 5), the score for each question, will be reported for every subject at each time point and will be summarized and plotted over time using descriptive statistics.
- For PGI-S, the score will be reported for every subject at each time point and will be summarized and plotted over time using descriptive statistics.
- For PGI-C, the score will be reported for every subject at Week 12 and Week 24 (EOT) and will be summarized and plotted over time using descriptive statistics.
- Missing data will not be imputed for any analyses.

## 15 APPENDICES

### 15.1 Appendix A: Preliminary Table of Contents for Tables, Listings, Figures for Safety and Efficacy

#### **Tables: Demographics, Baseline Characteristics, Analysis Populations/Subject Accountability, Medical History, Hyperhidrosis History, Concomitant Medications**

- Table 14.1.1 Analysis Populations / Subject Accountability
- Table 14.1.2.1 Demographics, Baseline Characteristics - Safety
- Table 14.1.2.2 Demographics and Baseline Characteristics- PK
- Table 14.1.3 Medical History and Hyperhidrosis History – Safety
- Table 14.1.4 Concomitant Medications - Safety

#### **Efficacy Tables – Safety Population**

- 14.2.1 Summary of HDSM-Ax and HDSM-Ax, Child Measurements and Changes from Baseline (All)
- 14.2.2 Summary of HDSM-Ax and HDSM-Ax, Child Anchors and Change from Baseline over Time (All)
- 14.2.3 Summary of PGI-S score and Change from Baseline over Time (All)
- 14.2.4 Summary of PGI-C score and Change from Baseline over Time (All)

#### **Efficacy Figures – Safety Population**

- Figure 14.2.1 Mean Changes from Baseline Over Time in HDSM-Ax, Child and HDSM-Ax (All)
- Figure 14.2.2 Mean Observed Values over Time in HDSM-Ax, Child and HDSM-Ax (All)
- Figure 14.2.3 Mean Changes from Baseline Over Time in HDSM-Ax, Child and HDSM-Ax Anchors (All)
- Figure 14.2.4 Mean Observed Values over Time in HDSM-Ax, Child and HDSM-Ax Anchors (All)
- Figure 14.2.5 Mean Changes from Baseline Over Time in PGI-S (All)
- Figure 14.2.6 Mean Observed Values over Time in PGI-S (All)
- Figure 14.2.7 Mean Changes from Baseline Over Time in PGI-C (All)
- Figure 14.2.8 Mean Observed Values over Time in PGI-C (All)

#### **Safety Data – Safety Population**

#### **Displays of Adverse Events**

- Table 14.3.1.1 Incidence of Treatment Emergent Related Adverse Events by Severity
- Table 14.3.1.2 Incidence of Serious Treatment Emergent Adverse Events by Severity
- Table 14.3.1.2 Incidence of Serious Treatment Emergent Related Adverse Events by Severity

### **Abnormal Laboratory Value Listing (each Subject) – Safety Population**

- Table 14.3.4.1 Clinical Chemistry Laboratory Summary
- Table 14.3.4.2 Clinical Chemistry Laboratory Values Shift Tables
- Table 14.3.4.3 Hematology Laboratory Summary
- Table 14.3.4.4 Hematology Laboratory Values of Interest Shift Tables
- Table 14.3.4.5.1 Urinalysis Laboratory Summary (Continuous Results)
- Table 14.3.4.5.2 Urinalysis Laboratory Summary (Categorical Results)
- Table 14.3.4.5.3 Incidence and Severity of Application Site Burning – Shift Table
- Table 14.3.4.5.4 Incidence and Severity of Application Site Itching – Shift Table
- Table 14.3.4.5.5 Incidence and Severity of Application Site Dryness – Shift Table
- Table 14.3.4.5.6 Incidence and Severity of Application Site Scaling – Shift Table
- Table 14.3.4.5.7 Incidence and Severity of Application Site Erythema – Shift Table

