Study Day (\pm days)/ Visit	Day 1/ Visit 1	Day 28 (\pm 3)/ Visit 2	Day 56 (\pm 5)/ Visit 3	Day 84 (\pm 5)/ Visit 4	Day 112 (\pm 5)/ Visit 5	Day 140 (\pm 5)/ Visit 6	Day 168 (\pm 5)/ Visit 7	Day 182 (\pm 5)/ Visit 8
Consent/Assent Refer to Section 6.1	X							
Inclusion/Exclusion criteria Refer to Sections 5.1 and 5.2	X							
Demographics Refer to Section 6.2	X ^a							
Height/Weight Refer to Section 6.5	X ^a							
Abbreviated Physical Examination Refer to Section 6.4	X ^b	X					X	X
Medical/Medication History Refer to Section 6.3	X ^b							
Vital Signs Refer to Section 6.7	X ^b	X	X	X	X	X	X	X
HDSM-Ax and HDSM-Ax, Child Refer to Section 6.8	X ^a	X	X	X	X	X	X	X
PGI-S Refer to Section 6.10	X ^{a,b}	X	X	X	X	X	X	X
PGI-C Refer to Section 6.11				X			X	
Safety laboratory testing Refer to Section 6.12.4.2	X ^{a,b}	X					X	X ^d
Pregnancy testing (females only) Refer to Section 6.12.4.1	X ^b	X	X	X	X	X	X	

Description	Screening/ Enrollment	Treatment					End of Treatment/Early Termination	End of Study
		Week 0	Week 4	Week 8	Week 12	Week 16		
Study Day (\pm days)/ Visit	Day 1/ Visit 1	Day 28 (\pm 3)/ Visit 2	Day 56 (\pm 5)/ Visit 3	Day 84 (\pm 5)/ Visit 4	Day 112 (\pm 5)/ Visit 5	Day 140 (\pm 5)/ Visit 6	Day 168 (\pm 5)/ Visit 7	Day 182 (\pm 5)/ Visit 8
Pharmacokinetic sampling Refer to Section 6.12.5	X ^b	X ^c					X ^c	
12-lead ECG Refer to Section 6.8	X ^b	X					X	X ^d
Concomitant Medications Refer to Section 6.13	X ^b	X	X	X	X	X	X	X
AE Assessment Refer to Section 10	X ^b	X	X	X	X	X	X	X
Application Site Tolerability Assessment Refer to Section 6.6	X ^b	X	X	X	X	X	X	
Dosing Refer to Sections 8.4 and 8.5 and Study drug application and dosing diary card completion Refer to Appendix C								
Compliance Refer to Section 8.5	X ^b	X	X	X	X	X	X	
Study Drug Dispensing Refer to Section 8.3	X	X	X	X	X	X		

^a Baseline data (prior to first dose) collected under BBI-4000-CL-105 will be carried over to the current study.

^b Data collected at End of Treatment (Day 8 [\pm 1 day]) under BBI-4000-CL-105 will be carried over to the current study.

^c Collection \geq 12 hours from evening application of drug.

^d Only collect if abnormal at Visit 7/Early Termination Visit.

TABLE OF CONTENTS

AGREEMENT OF INVESTIGATOR COMPLIANCE	3
ABBREVIATIONS	4
PROTOCOL SYNOPSIS	6
SCHEDULE OF ACTIVITIES.....	12
1 INTRODUCTION	18
1.1 Background	18
1.2 Rationale.....	18
1.3 Risk / Benefit Assessment.....	18
3 STUDY OBJECTIVES AND ENDPOINTS	18
3.1 Objectives	18
3.1.1 Primary Objectives	18

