6.6 Application Site Tolerability Assessment

Application site tolerability assessments will be evaluated through assessment of symptoms at the drug-application site. These assessments are to be performed for each axilla individually. Subject assessments will be made prior to the Investigator assessments ([Appendix F](#)).

Subject Local Tolerability Assessments: Subjects will be queried about whether any symptoms of burning, stinging, or itching occurred at the drug-application site within the previous 24 hours and further whether any such symptoms persisted longer than 1 hour following study drug application. Standardized scales will be used to describe specifically the severity of any burning, stinging or itching ([Appendix F](#)).

Investigator Local Tolerability Assessments: Investigators will observe for the existence of any significant local symptoms of scaling or erythema at the drug-application site. Significant local symptoms are defined as those not ordinarily observed following application of a topical product. Standardized scales will be used to describe specifically the severity of any erythema or scaling ([Appendix F](#)).

Local tolerability signs and symptoms that result in the subject's requiring a concomitant therapy, interruption of treatment, or discontinuation from the study, will also be reported as an AE.

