## Figure 1 Study Schematic

#### 4 SCHEDULE OF ACTIVITIES

Description With Protocol Reference	Screening/ Enrollment	Treatment					End of Treatment/Early Termination	End of Study
Week	Week 0	Week 4	Week 8	Week 12	Week 16	Week 20	Week 24	Week 26
Study Day ( $\pm$ days)/ Visit	Day 1/ Visit 1	Day 28 ( $\pm$ 3)/ Visit 2	Day 56 ( $\pm$ 5)/ Visit 3	Day 84 ( $\pm$ 5)/ Visit 4	Day 112 ( $\pm$ 5)/ Visit 5	Day 140 ( $\pm$ 5)/ Visit 6	Day 168 ( $\pm$ 5)/ Visit 7	Day 182 ( $\pm$ 5)/ Visit 8
Consent/Assent Refer to Section 6.1	X							
Inclusion/Exclusion criteria Refer to Sections 5.1 and 5.2	X							
Demographics Refer to Section 6.2	X a							
Height/Weight Refer to Section 6.5	X a							
Abbreviated Physical Examination Refer to Section 6.4	X b	X					X	X
Medical/Medication History Refer to Section 6.3	X b							
Vital Signs Refer to Section 6.7	X b	X	X	X	X	X	X	X
HDSM-Ax and HDSM-Ax, Child, Refer to Section 6.8	X a	X	X	X	X	X	X	X
PGI-S Refer to Section 6.10	X a,b	X	X	X	X	X	X	X
PGI-C Refer to Section 6.11				X			X	
Safety laboratory testing Refer to Section 6.12.4.2	X a,b	X					X	X d
Pregnancy testing (females only) Refer to Section 6.12.4.1	X b	X	X	X	X	X	X	
PK sampling Refer to Section 6.12.5	X b	X c					X c	

Description With Protocol Reference	Screening/ Enrollment	Treatment					End of Treatment/Early Termination	End of Study
Week	Week 0	Week 4	Week 8	Week 12	Week 16	Week 20	Week 24	Week 26
Study Day ( $\pm$ days)/ Visit	Day 1/ Visit 1	Day 28 ( $\pm$ 3)/ Visit 2	Day 56 ( $\pm$ 5)/ Visit 3	Day 84 ( $\pm$ 5)/ Visit 4	Day 112 ( $\pm$ 5)/ Visit 5	Day 140 ( $\pm$ 5)/ Visit 6	Day 168 ( $\pm$ 5)/ Visit 7	Day 182 ( $\pm$ 5)/ Visit 8
12-lead ECG Refer to Section 6.8	X b	X					X	X d
Concomitant Medications Refer to Section 6.13	X b	X	X	X	X	X	X	X
AE Assessment Refer to Section 10	X b	X	X	X	X	X	X	X
Application Site Tolerability Assessment Refer to Section 6.6	X b	X	X	X	X	X	X	
Dosing, Refer to Sections 8.4 and 8.5 and Study drug application and dosing diary card completion Refer to Appendix C								
Compliance Refer to Section 8.5	X b	X	X	X	X	X	X	
Study Drug Dispensing Refer to Section 8.3	X	X	X	X	X	X		

a Baseline data (prior to first dose) collected under Study BBI-4000-CL-105 will be carried over to the current study.

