b Data collected at EOT (Day 8 [ $\pm$ 1 day]) under Study BBI-4000-CL-105 will be carried over to the current study.

c Collection  $\geq$ 12 hours from evening application of drug.

d Only collect if abnormal at Visit 7/Early Termination Visit.

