## **12.4 Derived and Transformed Data**

### **Baseline**

The Baseline (Day 1, pre-dose) measurement of a variable is the latest non-missing measurement before the first dose of study drug in Study BBI-4000-CL-105

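### SAP Appendix A lists application-site tolerability tables only as shift tables, which need a pre-dose score that the schedules do not carry over and leave out the by-visit severity counts called for in SAP 13.3.1

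*SAP*

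**What the plan says.** - **Planned displays.** SAP section 15.1 is headed "Appendix A: Preliminary Table of Contents for Tables, Listings, Figures for Safety and Efficacy". It lists five application-site tables, 14.3.4.5.3 to 14.3.4.5.7, for burning, itching, dryness, scaling and erythema. All five are shift tables; the first is "Incidence and Severity of Application Site Burning – Shift Table". The only other application-site output listed is Listing 16.2.7.7.
- **Analysis text.** SAP 13.3.1 describes tolerability as the number and percentage of subjects at each severity, taking the worse axilla, by parameter and visit, with subject and investigator ratings in separate tables. Protocol 11.4.1 likewise describes severity at each visit. Both sections prescribe shift tables for laboratory parameters only.
- **Baseline.** SAP 12.4 says the baseline value "is the latest non-missing measurement before the first dose of study drug in Study BBI-4000-CL-105". Protocol 11.3.1 gives the same definition.
- **What is carried over.** In both Schedules of Activities the row "Application Site Tolerability Assessment Refer to Section 6.6" has footnote b alone at Week 0. Footnote b begins "Data collected at End of Treatment (Day 8" in the protocol and "Data collected at EOT (Day 8" in the SAP. Footnote a, "Baseline data (prior to first dose) collected under BBI-4000-CL-105 will be carried over to the current study", is attached to demographics, height and weight, HDSM-Ax, PGI-S and safety laboratory tests (the last two carry both footnotes). It is not attached to tolerability.
- **Missing data.** Under SAP 12.6, a missing tolerability score is not imputed.

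**The concern.** Incidence and severity of burning, itching, stinging, scaling and erythema is the first primary safety endpoint listed (Protocol 3.2.1.1, SAP 7.2.1.1). The table list and the analysis text call for different displays of it. The listed display depends on a reference score that the schedules do not supply, and no section names the reference visit for these tables.

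A programmer working from Appendix A has three choices: import a pre-dose score from CL-105 if one exists, leave the baseline missing, or use the Week 0 value, which is the Day 8 score on drug. The third is the easiest slip, because Day 8 is the only tolerability value in the Week 0 column. It would measure change from a point at which subjects had already been treated for about a week, so a reaction that began in that week and persisted would not register as a change.

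**Working it through.** The plan states no figure on this point. The limit of 24 subjects is the CL-105 enrolment cap, not the result of a calculation. The check is therefore a comparison of sections, followed by an illustration.

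**Sections side by side**

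| Element | SAP 13.3.1 | SAP Appendix A |
|---|---|---|
| Format | Count and % by severity, parameter and visit | Shift tables only |
| Signs | Burning, itching, stinging, scaling, erythema | Burning, itching, dryness, scaling, erythema |
| Reference score needed | None | Pre-first-dose CL-105 score (SAP 12.4) |
| Score carried over in the schedules | Day 8 can be shown as a visit | Day 8 does not meet SAP 12.4 |

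Dryness is not among the scales in SAP Appendix E or Protocol Appendix F. Stinging is. Listing 16.2.7.7 has the same error.

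**The three choices**

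1. *Import a pre-dose CL-105 score.* This agrees with SAP 12.4, but these documents do not say whether such a score was recorded.
2. *Leave the baseline missing.* This follows from footnote b together with SAP 12.6. The shift tables then have no baseline classification.
3. *Use Day 8.* This contradicts SAP 12.4 and Protocol 11.3.1.

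**Illustration of the third choice**

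All rates here are assumed. Take 24 subjects who score 0 before any drug. Let k have a non-zero score at Day 8. By Week 4 half of these persist unchanged (k/2) and half fade to 0 (k/2), and 2 other subjects develop a new reaction.

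- Worsened at Week 4, pre-dose reference: (k/2 + 2)/24
- Worsened at Week 4, Day 8 reference: 2/24
- Improved at Week 4, Day 8 reference: k/2 subjects
- Ongoing reaction classed as no shift, Day 8 reference: k/2 subjects
- Non-zero score at Week 4 in the by-visit count: (k/2 + 2)/24
- Any reaction at Day 8 or Week 4 (worst score): (k + 2)/24

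| k | Worsened, pre-dose ref. | Worsened, Day 8 ref. | Improved, Day 8 ref. | No shift but reacting, Day 8 ref. | By-visit count, Week 4 | Worst score above 0 |
|---|---|---|---|---|---|---|
| 2 | 3/24 = 12.5% | 2/24 = 8.3% | 1 | 1 | 3/24 = 12.5% | 4/24 = 16.7% |
| 4 | 4/24 = 16.7% | 2/24 = 8.3% | 2 | 2 | 4/24 = 16.7% | 6/24 = 25.0% |
| 6 | 5/24 = 20.8% | 2/24 = 8.3% | 3 | 3 | 5/24 = 20.8% | 8/24 = 33.3% |

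With a pre-dose reference no subject improves, because all start at 0.

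The by-visit count does not depend on the reference. It does not by itself give incidence over the study: for k = 4 it shows 4/24 at Day 8 and 4/24 at Week 4, while 6 different subjects have reacted.

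**Would any subject be affected?** If a share q of subjects has a non-zero Day 8 score, the expected number is 24q, and with independent subjects the chance of at least one is 1 − (1 − q)^24. For q = 5%, 10% and 20% the expected numbers are 1.2, 2.4 and 4.8, and the chances are 0.71, 0.92 and 0.995.

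**The case against.** The case against is substantial.

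- **The body text already asks for the right display.** SAP 13.3.1 requires by-visit severity counts, Listing 16.2.7.7 gives individual data, and Appendix A is labelled preliminary. This stands, and it limits the point to a conflict between text and table list. It does not remove the conflict, because no listed table delivers the counts.
- **A shift table does not erase a persistent reaction.** A subject graded 3 at both times sits visibly in the 3-to-3 cell, and the visit margin shows absolute severity. This stands for a full cross-tabulation. The SAP does not specify the shell, and the margin is lost if subjects without a baseline are left out.
- **Footnote b does not prove that no pre-dose score will be used.** Vital signs also carry footnote b alone, yet SAP 13.3.1 plans changes from baseline for them. This stands: the source of the baseline is unclear, and not only for tolerability.
- **A pre-drug score is possible for most items.** The scales include a zero grade, and scaling and erythema can be rated at any time. This largely stands. Only the sub-question on "further whether any such symptoms persisted longer than 1 hour following study drug application" presupposes a dose.
- **Other safeguards exist.** Exclusion 1 bars clinically significant local reactions at entry. Local signs that lead to concomitant therapy, interruption or discontinuation are also reported as adverse events (Protocol 6.6). This stands, so any masking concerns reactions not judged clinically significant. Those still count toward an endpoint graded 0 to 4.

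A reader might infer that the plan measures tolerability from an on-drug baseline and so hides early, lasting reactions. The documents do not support that. No section names Day 8 as the reference, and SAP 12.4 rules it out.

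**Conclusion.** The point holds as an unresolved conflict in how the first primary safety endpoint is displayed. The table list departs from SAP 13.3.1, its format needs a score that the schedules do not carry over, and its list of signs is wrong in two places. These findings rest on the documents alone.

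The bias is conditional. It arises only if Day 8 is taken as baseline against SAP 12.4, and then it runs one way: fewer subjects appear to worsen and some appear to improve. Its size is unknown. The 8.3% against 12.5% to 20.8% in the illustration comes from assumed reaction rates, half of the Day 8 reactions persisting, and pre-dose scores of 0. With at most 24 subjects, each one misread is 1/24, or about 4 percentage points. The change is worth making before the SAP is finalised, because it is small and the affected endpoint is primary.

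**What to change.** 1. Replace shells 14.3.4.5.3 to 14.3.4.5.7 with the SAP 13.3.1 tables: number and percentage at each severity, maximum of the two axillae, by visit, for burning, stinging, itching, scaling and erythema.
2. Show CL-105 Day 8 in these tables as an on-treatment visit.
3. Add the worst on-treatment severity per subject for each sign. This gives the incidence that the endpoint names.
4. Keep a shift table only where a true pre-first-dose CL-105 score exists, name that score as the reference, and leave the baseline missing otherwise. State in SAP 13.3.1 that Day 8 is not used as baseline.
5. Remove dryness and add stinging, in the tables and in Listing 16.2.7.7.

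The cost is revised table and listing shells and one sentence in the SAP. No new data are needed.

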### **Other Safety Data Summaries – Safety Population**

- Table 14.3.5.1 Summary of Vital Signs
- Table 14.3.5.2 Summary of ECG parameters
- Table 14.3.5.3 Incidence of Out of Range ECG parameters
- Table 14.3.5.4 Summary of Status of ECGs (normal, abnormal not clinically significant, abnormal clinically significant)

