## 7.2 Endpoints

### 7.2.1 Primary Endpoints

#### 7.2.1.1 Safety

- Incidence and severity of application site burning, itching, stinging, scaling and erythema
- Incidence and severity of all AEs and their relationship to study drug
- Incidence of clinically meaningful change from baseline in safety laboratory parameters, physical examination, 12-lead ECGs and vital signs
- Proportion of subjects who discontinue treatment due to an AE

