### 13.3 Primary Analyses

#### 13.3.1 Safety

Safety evaluations will consist of AEs, application site local tolerability, physical examinations, vital signs, ECGs, and laboratory measurements (hematology, chemistry, and urinalysis).

- Adverse events:
  - Adverse events will be mapped to standard terms, i.e., MedDRA System Organ Class and Preferred Term.
  - Adverse events that occurred during the screening period will be listed separately and will not be included in the AE tabulations.
  - Adverse events that start on or after first dose will be considered a TEAE. At each post-baseline visit, the number and proportion of subjects reporting any given TEAE will be tabulated by severity; each subject will be counted only once according to the worst severity reported up to the current visit. Separate tables will be constructed for (a) all reported TEAEs, (b) protocol treatment related TEAEs, (c) serious TEAEs, and (d) TEAEs leading to protocol treatment discontinuation.
- At each applicable visit, local tolerability (burning, itching, stinging, scaling, and erythema at either axilla) will be described by severity as defined in Appendix E. Subject and Investigator assessments will be included in separate tables and listings, with the count and percentage of subjects within each severity (maximum severity assessed at either axilla) presented by parameter and visit.
- Vital signs will be summarized similarly as for laboratory parameters but without shift tables.
- Laboratory parameters will be descriptively summarized (mean, SD, median, minimum, maximum) for values at each visit and for changes from baseline at each subsequent visit. In addition, at each post baseline visit, parameter status (low, normal, high) will also be summarized as shift tables vs. baseline status.
- Descriptive statistics and/or frequency tables will be prepared as appropriate for physical examinations, and ECG (HR, QTcF, PR, and QRS) parameters, and abnormalities (e.g., normal; abnormal, not clinically significant; abnormal, clinically significant).
- Concomitant medications will be mapped according to the World Health Organization Drug Dictionary (WHODD) and will be presented in data listings.

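### ECG change from baseline is part of the primary safety endpoint, but the SAP specifies no change-from-baseline or shift display for ECGs

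*SAP*

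**What the plan says.** SAP 7.2.1.1 lists among the primary safety endpoints "Incidence of clinically meaningful change from baseline in safety laboratory parameters, physical examination, 12-lead ECGs and vital signs". Protocol 3.2.1.1 also names 12-lead ECGs in this endpoint.

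SAP 13.3.1 treats three kinds of safety data differently:

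- **Laboratory parameters** are summarised "for values at each visit and for changes from baseline at each subsequent visit", and "parameter status (low, normal, high) will also be summarized as shift tables vs. baseline status".
- **Vital signs:** "Vital signs will be summarized similarly as for laboratory parameters but without shift tables".
- **ECGs** share a sentence with physical examinations: "Descriptive statistics and/or frequency tables will be prepared as appropriate for physical examinations, and ECG (HR, QTcF, PR, and QRS) parameters, and abnormalities". The abnormality categories given as examples are normal, abnormal but not clinically significant, and abnormal and clinically significant.

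SAP Appendix A (15.1), headed as preliminary, lists three ECG tables. Table 14.3.5.2 summarises ECG parameters. The other two are "Table 14.3.5.3 Incidence of Out of Range ECG parameters" and "Table 14.3.5.4 Summary of Status of ECGs (normal, abnormal not clinically significant, abnormal clinically significant". Listings 16.2.7.4 and 16.2.7.5 show individual ECGs and ECG abnormalities.

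SAP 12.4 defines baseline as the last non-missing value before the first dose in Study BBI-4000-CL-105. In the Schedule of Activities the Week 0 ECG carries footnote b only, meaning the CL-105 Day 8 (± 1 day) record. Protocol 6.8 says the same.

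**The concern.** The endpoint is an incidence of change, so each child has to be compared with his or her own baseline. A table of how many ECGs are abnormal, or how many parameters are out of range, does not make that comparison. A child whose ECG was abnormal before treatment counts the same as one whose abnormality is new. A new case can be hidden when an old one resolves, and persisting old findings can be mistaken for incidence.

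The drug is an anticholinergic applied daily for up to 24 weeks by children and adolescents aged 9 to 17. ECG is a named part of a primary safety endpoint, so the planned tables should yield the ECG result directly.

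**Working it through.** The plan states no figure on this point. The sample size of up to 24 is carried over from CL-105 (SAP 11), so there is nothing to reproduce.

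**Step 1. Compare the analysis text with the table titles.**

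| Data | Change from baseline in SAP 13.3.1 | Shift table in SAP 13.3.1 | Titles in Appendix A |
|---|---|---|---|
| Laboratory | Yes | Yes | Summaries, plus shift tables for chemistry and hematology |
| Vital signs | Yes, by reference to laboratory data | Excluded | Summary only |
| ECG | Not stated | Not stated | Parameter summary, out-of-range incidence, status |

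A title that omits change proves little by itself. The vital signs title omits it too, but there the text of 13.3.1 supplies it. For ECGs neither text nor title does. Appendix A does label shift tables (laboratory and application-site) and change from baseline (efficacy) elsewhere.

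**Step 2. What status counts can show.** Let N be the number of subjects, b the number abnormal at baseline and w the number abnormal at a later visit. From b and w alone, the number of new abnormalities lies between max(0, w − b) and min(w, N − b). N = 24 is the maximum in SAP 11, with all subjects assumed to have both ECGs. The values of b and w are assumptions.

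| b | w | New cases | % of 24 | % of those normal at baseline (N − b) |
|---|---|---|---|---|
| 0 | 3 | exactly 3 | 12.5 | 12.5 |
| 2 | 3 | 1 to 3 | 4.2 to 12.5 | 4.5 to 13.6 |
| 3 | 3 | 0 to 3 | 0 to 12.5 | 0 to 14.3 |
| 4 | 4 | 0 to 4 | 0 to 16.7 | 0 to 20.0 |
| 5 | 5 | 0 to 5 | 0 to 20.8 | 0 to 26.3 |
| 8 | 8 | 0 to 8 | 0 to 33.3 | 0 to 50.0 |

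For b = w = 4, the lower bound is max(0, 4 − 4) = 0 and the upper is min(4, 24 − 4) = 4, with 4/24 = 16.7% and 4/20 = 20.0%. The bounds meet only when nobody or everybody is abnormal at one of the two times. A shift table gives one exact count in every case.

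**Step 3. Which ECG is the baseline.** SAP 12.4 requires a value from before the first CL-105 dose. The only ECG the schedule carries over is from CL-105 Day 8, after about 7 days of treatment. Laboratory tests carry both footnote a (CL-105 pre-dose) and footnote b (Day 8); ECG carries only b. Protocol 4.1 and SAP 3 call the Week 0 ECG pre-dose on Day 1, but Day 1 of this study is Day 8 of CL-105. A shift table built on that record would use an on-treatment reference and would miss changes arising in the first week.

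**The case against.** The strongest reply is that the plan does not rule out ECG change displays. Appendix A is preliminary and gives titles, not shells. Table 14.3.5.2 could contain changes, and the wording of 13.3.1 leaves room for them. The titles of Tables 14.3.5.3 and 14.3.5.4 do not say by visit, and the former uses the word incidence. This stands. A reader might infer that ECG change will never be analysed, or that the tables are fixed as prevalence by visit; the documents support only that a change or shift display is nowhere specified.

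Second, the listings show each subject's ECGs. With at most 24 subjects and scheduled ECGs at Weeks 0, 4 and 24 (Week 26 only if Week 24 was abnormal), new findings can be traced by hand. SAP 12.3.1 itself falls back on listings when a table is sparse. This reduces the consequence, so it would be wrong to infer that the information is lost. But a listing tabulates no incidence, and the endpoint is an incidence.

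Third, entrants must be in generally good health (Protocol 5.1), so few may be abnormal at baseline. If none are, the status counts give the number of new cases exactly. That is possible, but the plan should not depend on it.

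A reader might also infer a loss of precision for mean changes in QTcF or heart rate. That does not bear on this point: the endpoint is an incidence, and the SAP plans no ECG tests or confidence intervals.

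**Conclusion.** The point holds as a gap in specification. The primary safety endpoint includes ECG change from baseline, and neither SAP 13.3.1 nor the table list specifies a display that measures it. The laboratory data in the same section do get such displays.

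The size depends on how many children have an abnormal ECG at baseline, which the documents do not give. With an assumed 4 of 24 abnormal at both times, the uncertainty is 0 to 4 new cases (0% to 16.7%); with none abnormal at baseline it vanishes.

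Two limits apply. A reader might infer that the remedy needs no further data, or that no pre-treatment ECG exists. The documents support neither; they show only that the Day 8 ECG is carried over. Also, neither document says what makes an ECG change clinically meaningful, so shift tables and changes would make change visible without settling that criterion.

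**What to change.** Before database lock:

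1. In SAP 13.3.1, summarise HR, QTcF, PR and QRS as values and as changes from baseline at Weeks 4 and 24, as for laboratory parameters.
2. Make Table 14.3.5.4 a shift table of baseline status against status at each scheduled visit and against worst post-baseline status. Label Week 26 as repeat ECGs in a selected subset.
3. In Table 14.3.5.3, show subjects newly out of range separately from those already out of range at baseline.
4. State which ECG is the baseline. Import the pre-treatment CL-105 ECG if it exists. If it does not, label the Day 8 ECG as an on-treatment reference that cannot show first-week changes.

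The cost is SAP wording, one or two table changes and possibly importing one existing CL-105 record per subject, so at most 24 records. No new assessments of the children are needed.
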